***Tacrolimus Trough Level Monitoring:***

Tacrolimus whole blood trough levels will be measured prior to the morning dose on Visits 2, 3, and 4. Tacrolimus whole blood trough levels obtained from local laboratories will be used to ensure patient's treatment exposure is maintained in the therapeutic range.

**Concomitant Therapy:****Immunosuppressants:**

Only CellCept® (MMF, Roche Laboratories, Nutley, NJ), Myfortic® (MPS, Novartis Pharmaceuticals, East Hanover, NJ), including generic versions of each, or prednisone (or equivalent <10 mg/day) with choice and doses per SOC at the participating site are allowed (but not required). Patients receiving immunosuppressants should be on a stable dose throughout the treatment period from Visit 2 to Visit 3 of the study.

**CYP3A inhibitors or inducers:**

Whenever feasible, CYP3A inhibitors or inducers should be avoided; however clinical circumstances may necessitate using such agents. When this is the case, increased monitoring of tacrolimus concentrations is recommended.

**Other:**

All prophylaxis and other medications, including herbal products, will be allowed per SOC as long as ENVARSUS XR dosing remains stable throughout the treatment period from Visit 2 to Visit 3 of the study

## **Study Population:**

### Inclusion Criteria

1. Patients must be able to understand English and provide written informed consent;
2. Males and females between 18 and 80 years of age;
3. Recipients of a primary or secondary kidney transplant 4 weeks to 10 years prior to screening;
4. Patients receiving a stable dose (i.e., no dose adjustments) of TAC-IR for a minimum of 4-7 days at screening;
5. Patients with a screening tacrolimus trough level of 3-9 ng/mL, measured between Day -7 to 0;
6. Women of childbearing potential must have a negative urine pregnancy test at screening;
7. Patients must be willing to commit to and comply with the schedule of study visits.
8. The patient is not scheduled to begin any new medication that could interfere with tacrolimus blood levels, including prescription and over-the-counter medications, herbal, or food supplements (including grapefruit and pomegranate products), or medications listed in [Appendix 1](#).

### Exclusion Criteria

1. Recipients of any transplanted organ other than kidney;
2. Patients with an estimated glomerular filtration rate (eGFR) (modified diet in renal analysis 4 [MDRD4]) <25 mL/min at screening;
3. Patients with significant visual impairments affecting their ability to complete the study requirements and assessments: patient's vision is 20/200 or worse;
4. Patients with significant hearing impairments affecting their ability to complete the study requirements and assessments, based on Investigator discretion;

---

 Patients with visual aids (glasses or contact lenses) should be considered, provided their vision is adequately improved with the use of the aid.

5. Patients with any severe medical condition (including infection) requiring acute or chronic treatment that in the Investigator's opinion would interfere with study participation;
6. Patients who have a history of any of the following, based on documentation of clinical conditions and concomitant medications in the medical records:
  - Cognitive decline associated with stroke, per Investigator discretion
  - Dementia
  - Resected or existing brain tumor
  - Acute or chronic bipolar psychosis or schizophrenia per Investigator discretion ☐
  - Mental retardation
  - Moderate or severe traumatic brain injury
  - Failure of any major organ other than the kidneys (e.g., end-stage liver disease)
  - Known non-adherence (defined as documentation in the patient chart of multiple missed visits and/or medication doses) which in the investigator's opinion would interfere with the objectives of the study
7. Patients with medical history of hypertension or diabetes which is unmanageable by medically approved intervention (e.g., medication/diet) as assessed by the Investigator;
8. Patients with acute or chronic depression, corresponding to a score of  $\geq 20$  (corresponding to moderate depression) on the Beck Depression Inventory (BDI-II) at screening;
9. Patients who are taking any acute or chronic medications that may impact reaction time, memory, or sleep habits, based on Investigator discretion;
10. Patients on concurrent immunosuppression with MMF (CellCept) or MPS delayed release tablets (Myfortic), or generic versions of these medications, as per SOC, who have not been on stable doses (i.e., no dose adjustments or formulation change) for at least 4-7 days prior to screening;
11. Patients receiving prednisone or equivalent  $>10$  mg/day;
12. Patients with an episode of biopsy-proven or suspected acute rejection that requires treatment within 3 months of screening;

 Patients with hearing aids should be considered, provided their hearing is adequately improved with the use of the aid.

13. Patients who are being actively treated for cancer (with the exception of non-invasive basal cell or cutaneous squamous cell carcinoma);
14. Patients known to be human immunodeficiency virus (HIV) positive;
15. Patients with any form of current drug or alcohol abuse as assessed by the Investigator;
16. Patients who were treated with any other investigational agent within 1 month prior to screening;
17. Pregnant or nursing women or women planning to become pregnant, where pregnancy is defined as a state of the female patient after conception and until the termination of gestation, confirmed by a positive urine pregnancy laboratory test; women of childbearing potential, defined as all women physiologically capable of becoming pregnant who are unwilling to use a defined SOC birth control method; UNLESS they are:
  - Women whose career, lifestyle, or sexual orientation preclude intercourse with a partner
  - Women whose partners have been sterilized by medically approved means

#### **Criteria for Withdrawal:**

Patients have the right to withdraw from the study at any time for any reason without penalty or prejudice. The Investigator also has the right to withdraw patients from the study if he/she feels it is in the best interest of the patient (see [Section 8.3.1](#)). For early withdrawal patients, an early withdrawal visit will be scheduled.

A patient may be withdrawn from the study treatment by the Investigator if: (1) the Investigator feels it is not in the patient's best interest to continue in the study, (2) the patient fails to follow the Investigator's instructions, (3) the patient experiences an adverse reaction that requires other medical treatment, or (4) the patient becomes pregnant.

#### **Evaluation Criteria:**

The primary endpoint is:

- Change in cognitive function from Visit 2 to Visit 3, as measured by the Global Composite Score on the Repeatable Battery for the Assessment of Neuropsychological Status (RBANS) , or the global composite score of the Covid-19 Telephone Battery, should that be the primary outcome battery that we employ. The secondary endpoints are as follows:

- Change in cognitive function from Visit 2 to Visit 3, as measured by the following:
- Trail Making Test A & B ([TMT-A, TMT-B] visual attention/executive functioning)
- Change in QoL from Visit 2 to Visit 3 and from Visit 2 to Visit 4, as measured by WHODAS.
- Assessment of Patient Global Impression of Improvement and Clinical Global Impression of Improvement (PGI-I and CGI-I, respectively) at Visit 3.
- Change in quality of sleep from Visit 2 to Visit 3, as measured by the Pittsburgh Insomnia Rating Scale-20 Item Version (PIRS-20)
- Safety evaluation will include adverse events (AEs), serious AEs (SAEs), vital sign measurements, and physical examinations.

Should safety precautions for COVID-19 preclude us from seeing patients in person, neurocognitive function will be assessed via a phone battery derived from standard cognitive tests and proven feasible and valid to assess memory, attention, reasoning, and executive function. These will include the TICS (Telephone interview for Cognitive Testing), WAIS-IV (Digit Span and Similarities), WMS-IV (Logical Memory I & II), Controlled Oral Word Association (COWA), and Hayling Sentence Completion. Psychological status will be assessed using the Beck Depression Inventory II (BDI-II) and the Posttraumatic Stress Disorder-8 (PTSD-8). Quality of life will be assessed using the WHODAS. Age, race, sex, and level of education will also be collected.

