### **Analysis Sets:**

*Intent-to-Treat (ITT) Dataset:* Includes all patients who are enrolled. The efficacy analyses will be performed using this dataset.

*Evaluable Dataset:* Includes all patients who are enrolled and received at least one dose of ENVARSUS XR and within targeted trough level of 3-9 ng/mL. In addition, the patients must have baseline and post-conversion evaluation for at least one of the cognitive tests (RBANS, TMT-A/TMT-B) without major protocol violation/deviation that would affect the cognitive measurement. The efficacy analyses will also be performed using this dataset.

*Safety Dataset:* Includes all patients who are enrolled and received at least one dose of ENVARSUS XR. The safety analyses will be performed using this dataset.

Patients whose tacrolimus trough level at Visit 3 (or as measured at other SOC visits between Visit 2 and Visit 3) is outside the tacrolimus suggested target trough level of 3-9 ng/mL will still remain in the study. If a dose adjustment is required, the patient will be required to be on a stable dose of ENVARSUS XR (no dose adjustment) for a minimum of 4 days before Visit 3 assessments are performed (i.e., if a dose adjustment is medically necessary and occurs anytime between Visits 2 and 3 there should be a minimum of 4 days on a stable ENVARSUS XR dose before the Visit 3 assessments can take place). However, they will not be evaluable and will be included in the ITT population.

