| Day Number                                            | Day -30 to -1   | Day 0 a | Month 4 ± 30 days. | Month 8 ± 30 days | As needed b                      | When withdrawn c |
| TMT-A, TMT-B (visual scanning speed/visual attention) |                 | X                  | X                  | X                 |                                             | X                           |
| RBANS                                                 |                 | X                  | X                  | X                 |                                             | X                           |

|                                                                                             |  |                |   |   |   |   |
|---------------------------------------------------------------------------------------------|--|----------------|---|---|---|---|
| Telephonic/Virtual Covid-19 battery (to be employed if in-person testing is deemed unsafe). |  | X              | x | X |   | X |
| CGI-I                                                                                       |  |                | X | X |   | X |
| Safety monitoring                                                                           |  | X f | X | X | X | X |
| Prescribe ENVARSUS XR g                                                          |  | X h | X | X | X |   |
| Dose administration record                                                                  |  | X              | X | X | X | X |
| Study drug/reconciliation                                                                   |  |                | X | X |   | X |

Abbreviations: N/A = not applicable; eGFR = estimated glomerular filtration rate; CBC = Complete blood count; SOC = standard of care; BDI-II = Beck Depression Inventory; PGI-I = Patient's Global Impression of Improvement; WHODAS = World Health Organization Disability Assessment Schedule 2.0; PIRS-20 = Pittsburgh Insomnia Rating Scale; TMT-A/TMT-B = Trail Making Test A & B; CGI-I = Clinical Global Impression of Improvement;

a If both Visits 1 and 2 are combined, all items denoted by an 'X' in the table for both Visits 1 and 2 must be completed at this combined screening and enrollment visit. Only need to capture start date of ENVARSUS XR.

b Anytime between Visit 3 and last dose of ENVARSUS XR

c As soon as possible following last dose of ENVARSUS XR

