## **6.2 Study Endpoints**

### **6.2.1 Primary Efficacy Endpoint**

The primary efficacy endpoint is the change in cognitive function from Visit 2 to 3 as measured by the Global Cognition Score on the RBANS, a composite score reflecting performance in areas of immediate and delayed memory, visuospatial construction, language, and attention.

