## 14.1 Sample Size

The study aims to enroll approximately 60 patients. With an expected drop-out rate of 10% to 15%, a maximum of fifty-two (52) evaluable patients are expected to reach the end of study.

In order to detect an effect size of 0.5 with 80% power and a one-sided type I error rate of 0.025, a sample size of 34 evaluable patients is needed. (NOTE: We simply need at least 34 patients to have adequate power, but we anticipate approximately having 52, meaning that this study will almost certainly NOT be underpowered). An interim analysis will be conducted when data are available for 17 (half of 34) evaluable patients, to better estimate the variation and effect of the treatment.

The rule for sample size adjustment is as follows:

Denote the planned sample size  $(n) = n_1 + n_2$ , where  $n_1 = 17$ ; and  $n = 34$  (i.e.,  $n_2 = 17$ ) Let

$r=1.5$  be the rate of adjustment (which leads to the maximum sample size of 52). Define

$N_{\text{new}}$  (final sample size) as

$$N_{\text{new}} = \begin{cases} n_1 + K, & n \leq N \leq rn \\ n, & N < n \\ rn, & N > rn \end{cases}$$

where  $K$  is the calculated additional required sample size (beyond first 17 evaluable patients) and  $N$  is the calculated total required sample size based on the observed change and variation from the interim analysis.

The range of possible total sample sizes based on the interim analysis is from 34 and 52, i.e., the sample size remains at 34 if the adjusted estimate is below 34, and increases to a maximum of 52 if the adjusted estimate is beyond 52.

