#### **14.5.2 Secondary Efficacy Analysis**

Same methods as described above will be used to analyze other cognitive test scores or the global composite score of the Covid-19 Telephone Battery, should that be the primary outcome battery that we employ. In addition, the correlation among tests will be explored at each time point as well as the changes from baseline at Visit 3. Correlation coefficients and corresponding p-values will be displayed.

CGI-I and PGI-I will be summarized by number and percentages of patients in each category as well as combined categories of improvement (e.g., “Minimum improved”, “Much improved”, “Very much improved [CGI-I]/ Very much better [PGI-I]”).

PIRS-20 total score (sum of all 20 item scores with one missing item allowed) will be summarized at baseline and post-baseline visit. Absolute values at each time point as well as changes from baseline to post-baseline visit (i.e., Visit 3) will be analyzed.

All analyses will be based on ITT and Evaluable analysis datasets.

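### The primary endpoint may be RBANS or a telephone composite that is never defined, no rule fixes which, and one of two conflicting Evaluable definitions excludes telephone-tested patients

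*Combined protocol and SAP*

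**What the plan says.** - **Synopsis, Evaluation Criteria.** The primary endpoint is the Visit 2 to Visit 3 change in the RBANS composite, "or the global composite score of the Covid-19 Telephone Battery, should that be the primary outcome battery that we employ". The telephone tests are TICS, WAIS-IV Digit Span and Similarities, WMS-IV Logical Memory I and II, COWA and Hayling. They are used if COVID-19 precautions rule out in-person visits.
- **Schedule of Study Activities.** The telephone battery has its own row, marked at Visits 2, 3 and 4 and at early withdrawal, "to be employed if in-person testing is deemed unsafe".
- **Section 6.2.1.** The primary is the "change in cognitive function from Visit 2 to 3 as measured by the Global Cognition Score on the RBANS", with no alternative. Section 14.5.1 also names RBANS alone and gives a score derivation for RBANS only.
- **Section 14.5.2, under the secondary heading.** "Same methods as described above will be used to analyze other cognitive test scores or the global composite score of the Covid-19 Telephone Battery", followed by the same conditional clause as in the synopsis.
- **Synopsis, Analysis Sets.** Evaluable patients need a baseline and a post-conversion result on "at least one of the cognitive tests (RBANS, TMT-A/TMT-B"). Section 14.2 has a parallel definition that names no tests.
- **Section 14.3.4.** Missing data are not imputed unless that is specified.
- **Section 14.1.** The stated requirement is that "a sample size of 34 evaluable patients is needed". The inputs behind that number are given as follows: "In order to detect an effect size of 0.5 with 80% power and a one-sided type I error rate of 0.025". After allowing for dropout from about 60 enrolled, "a maximum of fifty-two (52) evaluable patients are expected" at the end of the study.

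**The concern.** A primary endpoint should be fixed before anyone can see which version gives the better answer. Here the synopsis leaves two candidates open and the body closes one of them, so the document does not agree with itself. The study is open-label. Section 14 asks for the full SAP only before database lock. Section 14.7 provides an interim estimate of effect once cognitive data on 17 evaluable patients are in, although the measure it names is a CPT-III score and not either battery.

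Two things are at stake. One is the error rate, if the choice of battery can follow the data. The other is the number of patients who have a usable paired score. A patient with RBANS at one visit and the telephone battery at the other has no change score on either. Keeping that patient in the ITT set does not help, because nothing is imputed.

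**Working it through.** **1. Where the sections disagree.**

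| Question | Synopsis | Body |
|---|---|---|
| Primary battery | RBANS or telephone composite | RBANS only (6.2.1, 14.5.1); conditional wording repeated under a secondary heading (14.5.2) |
| How the composite is formed | RBANS only | RBANS only (14.5.1) |
| Tests that make a patient evaluable | RBANS or TMT-A/TMT-B | none named (14.2) |
| Who decides on a switch, by when, for whom | not stated | not stated |
| Different modes at Visits 2 and 3 | not stated | not stated |

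The batteries do not measure the same thing. Section 10.2.2.5 includes Figure Copy, Line Orientation, Picture Naming and Coding in RBANS, and section 6.2.1 counts visuospatial construction as part of the primary. The synopsis describes the telephone battery as covering memory, attention, reasoning and executive function. Neither RBANS nor the Trail Making Tests are in it, so under the synopsis definition a patient tested only by telephone is not evaluable even if the telephone composite is primary.

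**2. The plan's own figure.** Inputs from section 14.1: effect size 0.5, one-sided alpha 0.025, power 80%. For a paired t-test on n patients, power = P(T > t(0.975, n−1)), where T is noncentral t with n−1 degrees of freedom and noncentrality 0.5√n. This gives 0.795 at n = 33 and 0.808 at n = 34, so the stated 34 is reproduced. The normal approximation, ((1.960 + 0.842)/0.5)² = 31.4, rounds up to 32.

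**3. Error rate if the better battery were chosen after seeing data.** With independent results (different patients on each battery), the one-sided rate is 1 − (1 − 0.025)² = 0.0494. If the two results are correlated, simulation with 2,000,000 draws gives:

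| Assumed correlation | 0.3 | 0.5 | 0.7 | 0.9 |
|---|---|---|---|---|
| One-sided type I error | 0.047 | 0.045 | 0.042 | 0.035 |

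For comparison, section 14.7 accepts an inflation of about 0.005 from the interim look. The worst case here adds 0.0494 − 0.025 = 0.0244.

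**4. Power if RBANS is primary and patients tested by telephone at Visit 2 or Visit 3 have no paired score.** The documents give no telephone share, so a range is assumed. The starting number is the 52 of section 14.1.

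| Assumed share lost | Patients left | Power |
|---|---|---|
| 0% | 52 | 0.943 |
| 10% | 52 × 0.9 = 46.8, so 47 | 0.919 |
| 20% | 52 × 0.8 = 41.6, so 42 | 0.886 |
| 30% | 52 × 0.7 = 36.4, so 36 | 0.831 |
| 40% | 52 × 0.6 = 31.2, so 31 | 0.768 |
| 50% | 52 × 0.5 = 26 | 0.688 |

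Power falls below 80% once fewer than 34 patients remain, that is, when more than 52 − 34 = 18 are lost (18/52 = 34.6%).

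**5. Can the two batteries be put on one scale?** (RBANS − 100)/15 has a normative SD of 1. A mean of six z-scores with common correlation r has SD √((1 + 5r)/6). At assumed r = 0.3 this is √(2.5/6) = 0.65, and at r = 0.5 it is √(3.5/6) = 0.76. The two are therefore not on one scale unless the telephone mean is rescaled.

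**The case against.** The strongest reply is that the trigger for telephone testing is external. It is a COVID-19 precaution, not a look at outcomes, and the study calls itself exploratory. Sections 6.2.1 and 14.5.1 are clear that RBANS is primary. Section 14.2 can be read to admit telephone tests, and efficacy is also analysed on the ITT set. With an assumed 30% of patients lost from 52, power is still 83%.

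Much of this is right, and it rules out several stronger readings that a reader might infer:

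- *That the plan intends a data-driven choice of primary.* It says nothing of the kind; it only fails to exclude one.
- *That section 14.5.2 makes the telephone composite secondary.* It repeats the conditional-primary clause under a secondary heading.
- *That the Evaluable set drops telephone-tested patients throughout.* Only the synopsis does so; section 14.2 conflicts with it.
- *That the battery is chosen afresh at each visit.* The schedule allows that reading, but the synopsis wording also fits a single study-level switch.
- *That the false-positive risk is 1 − 0.95² = 9.75%.* This counts errors in both directions. The study asks about improvement and is sized at one-sided 0.025, so 4.94% is the comparable figure.

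What does not fall away is that the synopsis and body disagree, the composite has no formula, and no rule covers a change of mode. An external trigger for using a battery is not a rule for which battery is primary. The ITT analysis cannot supply a paired score that was never measured.

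**Conclusion.** The point holds. The primary endpoint is not uniquely fixed, the telephone composite cannot be computed from the documents, and the two Evaluable definitions conflict.

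The two numerical consequences belong to different scenarios and must not be added together. The 0.049 is a ceiling that assumes independent results and a choice made after seeing data; it falls to 0.035 at an assumed correlation of 0.9. The power figures assume RBANS is primary, a starting number of 52, a true effect size of 0.5 and an assumed telephone share. Only telephone testing at Visit 2 or Visit 3 counts, because a telephone Visit 4 does not touch the primary change. The required number of patients, 34, does not change once one battery is fixed.

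**What to change.** Before any outcome data are reviewed:

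1. Name the Visit 2 to Visit 3 RBANS change as the single primary in the synopsis and sections 6.2.1, 14.5.1 and 14.5.2, with the telephone composite analysed separately as supportive. Alternatively, state a dated, study-level switching rule, made without outcome data, under which the telephone composite replaces RBANS. That rule should also say how patients whose Visit 2 was already on RBANS are treated.
2. Define the telephone composite, for example as the mean of normative z-scores of the listed tests. Name the norms, which the documents do not give, and say how Logical Memory I and II enter.
3. Use the same battery at Visits 2 and 3 for each patient wherever possible. State that mixed-mode patients have no primary change score, and report how many there are. A same-battery rule cannot rescue an RBANS patient who is unable to attend Visit 3.
4. Put one Evaluable definition in the synopsis and section 14.2. It should require baseline and post-conversion scores on the same battery, and include the telephone battery if that is primary.
5. Do not pool the batteries with a mode fixed effect. The scales differ (step 5 of the working), and in a single-arm change model the intercept is then the mean of one mode only. Without a stated contrast there is no defined overall test.

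The cost is protocol and SAP wording. The downside is that telephone-tested patients do not contribute to an RBANS primary, with the loss of power shown in step 4 of the working.
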